4.4 Study Visits

Subjects enrolled in this study will follow the below visit schedule according to their institutional standard of care for stroke patient follow-up.

- Baseline
- Randomization
- 24 hours (+/-12 hours) Post-Randomization
- 7 Days Post-Randomization or Discharge (whichever comes first)
- 30 Days (+/- 14 days) Post-Randomization Follow-up
- 90 Days (+/- 14 days) Post-Randomization Follow-up

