6.1 Analysis of Primary Endpoint

6.1.1 Definition of Analysis Samples

- Target Population
The target population for the POSITIVE trial is patients who are at least 18 who have a clinical diagnosis of Acute Ischemic Stroke who are ineligible for or refractory to treatment with IV-tPA and able to begin the thrombectomy procedure within a 6-12 hour time window of symptom onset or time last seen normal and as selected by physiologic imaging criteria.
- Intent to Treat Sample
As the primary analysis, all efficacy and safety outcome measures will be analyzed under the intent-to-treat (ITT) principle. Under this principle, the evaluable sample includes all subjects who are randomized. Each subject will be analyzed according to the treatment group to which they were assigned at randomization.
- Per Protocol Sample
In addition to the defined ITT analysis sample, a per-protocol sample is defined as a subset of the ITT sample. This sample will be used for secondary sensitivity analyses of the primary and secondary outcomes. The per-protocol sample will include all randomized subjects that do not have the following protocol violations or deviations:
 - a. Eligibility violation
 - b. Treatment crossover
 - c. Missing 90 day primary outcome (not including missing due to death prior to the 90 days)

7. General Statistical Considerations

The POSITIVE Trial is a multicenter, randomized, Phase III clinical trial investigating the safety and efficacy of endovascular mechanical thrombectomy administration in acute ischemic stroke patients ineligible for or refractory to treatment with IV-tPA presenting within a 6-12 hour time window as selected by physiologic imaging criteria compared to best MT. The primary hypothesis to be tested is that treatment with endovascular mechanical thrombectomy will improve outcomes at 90 days as compared to the best MT group. Each eligible subject will be randomized in a 1:1 ratio to either the endovascular mechanical thrombectomy or the best MT treatment group with a stratified randomization by NIHSS (<20 vs. ≥20) within each center to balance randomization. This variable was chosen because of the known association with outcome. Randomization will take place centrally through the web-based REDCap database system. The centrally controlled randomization will help ensure the treatment balance at any interim analysis as well as in the final analysis.

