7.1 Sample Size Estimation for the Primary Outcome

For this study design, power and sample size are computed by assuming that the true proportions of subjects with various mRS outcomes at the 90-day follow-up visit are consistent with the observed OR across all three recently published positive mechanical thrombectomy trials (EXTEND IA = 2.0, ESCAPE = 2.6, MR CLEAN = 1.67), which yields an average OR across all three of 2.1[37-39]. These data were used for the sample size calculation under the proportional odds ordinal logistic model. With the hypothesized OR of 2.1, a total sample size of 180 was estimated to achieve at least 80% power to detect the difference in mRS scores between the control and treatment groups. After accounting a loss of follow-up rate of 10%, the revised POSITIVE trial with a total of 200 patients would provide adequate power with moderate effect size.

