7.3 Missing Data and Imputation Methods

Under the ITT principle, all patients who are randomized are included in the analysis. Therefore, missing data, especially in the outcome measures, can be problematic. Every effort is to be made to keep all missing data, particularly the Day 90 outcomes, to a minimum. Despite the clinical sites' best efforts, some missing data may be inevitable mainly due to lost-to-follow-up (LTFU). The number and proportion of subjects eligible for and compliant with each follow-up examination will be presented. Subjects who withdraw from the study will be tabulated with reasons for withdrawal. Since the primary endpoint is defined using mRS, subjects deceased during study follow-up will be scored as mRS 6. Other subjects not completing the 90-day follow-up visit will be categorized for the primary endpoint using the mRS as of the last available follow-up visit or discharge (whichever is later). As a sensitivity analysis, we will also perform analysis after excluding subjects without 90-day follow-up evaluations. Additional details will be provided in the Statistical Analysis Plan (SAP).

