7.4 Secondary Statistical Analysis

7.4.1 Secondary Outcomes

- 90-day global disability in the 6-12 hr cohort assessed via the proportion of patients achieving a mRS of 0-2
- Proportion of patients with good functional recovery for the 6-12 hr cohort as defined by mRS 0-2 at 90 days

- Mortality at 30 and 90 days
- Intracranial hemorrhage with neurological deterioration (NIHSS worsening >4) within 24 hours of randomization
- Procedure related serious adverse events (SAE's)
- Arterial revascularization measured by TIC1 2b or 3 following device use

Secondary outcome endpoints will be compared between randomized groups in an ITT fashion; with overall Type I error controlled using hierarchical testing. That is, if statistical significance is observed on the primary effectiveness endpoint, the secondary clinical efficacy endpoints will then be tested in sequential fashion each at a two-sided alpha level of 0.05, with testing ceasing once a null hypothesis cannot be rejected. The statistical tests will be performed in the order specified above.

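### Per-protocol rule (c) should apply only to the 90-day mRS: as written it discards outcomes already observed and can raise per-protocol 30-day mortality

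*Combined protocol and SAP*

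**What the plan says.** Section 6.1.1 makes ITT the primary approach: "all efficacy and safety outcome measures will be analyzed under the intent-to-treat (ITT) principle". It then defines a per-protocol subset that leaves out patients with (a) an eligibility violation, (b) a treatment crossover, or (c) "Missing 90 day primary outcome (not including missing due to death prior to the 90 days". On its use the section says: "This sample will be used for secondary sensitivity analyses of the primary and secondary outcomes". No separate per-protocol set is given for individual outcomes.

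The secondary outcomes in section 7.4.1 include "Mortality at 30 and 90 days" and "Intracranial hemorrhage with neurological deterioration (NIHSS worsening >4) within 24 hours of randomization", together with procedure-related SAEs and reperfusion after device use. Apart from 90-day mortality and the mRS outcomes, most of these are known well before day 90. Section 4.4 schedules a 24-hour visit, a day-7 or discharge visit, and "30 Days (+/- 14 days) Post-Randomization Follow-up". Section 8 keeps data collected before a withdrawal of consent in the database.

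For the primary endpoint, section 7.3 states that "subjects deceased during study follow-up will be scored as mRS 6". It carries the last available mRS forward for other patients without a day-90 visit. As a sensitivity analysis it plans a run without patients who lack the day-90 evaluation. It leaves further detail to the SAP.

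**The concern.** Rule (c) suits the 90-day mRS, where death supplies a score and a missed visit does not. The same rule also governs outcomes that do not need a day-90 visit. A patient with a 24-hour scan and a completed day-30 visit who then misses day 90 is removed from the per-protocol analyses of hemorrhage, SAEs, reperfusion and 30-day mortality.

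For mortality the rule selects on the outcome. It can remove only patients not known to have died, so the denominator shrinks while the count of known deaths stays whole (rules (a) and (b) may still remove deaths).

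Rule (c) also mixes two things. Rules (a) and (b) concern who was eligible and what treatment was received, while (c) concerns follow-up. If per-protocol and ITT mortality disagree, a reader may credit crossover or ineligibility with a gap that comes from missed visits.

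**Working it through.** **Inputs from the protocol.** Section 7.1: 180 evaluable patients, 200 in total, OR 2.1 and 80% power; the allowance is introduced with "After accounting a loss of follow-up rate of 10" per cent. Section 1: 90-day mortality of 26% in the pilot thrombectomy series, and approaching 30% in untreated large vessel occlusion. **Assumed, because the protocol gives no figure:** 20% mortality at 30 days, the timing of loss, the vital status of lost patients, and loss by arm. Patients excluded under (a) or (b) are ignored throughout.

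**The plan's own figures.**
- The mean of the three cited odds ratios is (2.0 + 2.6 + 1.67)/3 = 2.09, given as 2.1.
- The proportional-odds (Whitehead) formula is N = 12(z_α + z_β)² / [ln(OR)² (1 − Σp̄³)]. With OR 2.1, 80% power, two-sided 0.05 (stated only for the secondary endpoints, assumed here for the primary), six categories and five assumed control distributions, it gives 177 to 183. The planned 180 is reproduced.
- Loss: 180/(1 − 0.10) = 200, so about 20 patients would lack the day-90 mRS.

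**24-hour and procedural outcomes.** Up to 20 of 200 patients leave these per-protocol analyses although nearly all would have the outcome on record.

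**30-day mortality.** Take 40 known deaths (20% of 200) and 20 patients lost by day 90, of whom k were known alive at day 30. Using all day-30 information gives 40/(180 + k). Rule (c) always gives 40/180 = 22.2%.

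| k | All day-30 data | Rule (c) | Inflation factor |
|---|---|---|---|
| 0 | 40/180 = 22.2% | 22.2% | 1.00 |
| 10 | 40/190 = 21.1% | 22.2% | 1.06 |
| 20 | 40/200 = 20.0% | 22.2% | 1.11 |

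The factor 1/0.90 = 1.11 is thus a ceiling, reached only if all loss comes after day 30.

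**90-day mortality.** Let D be the known deaths and f the fraction of the 20 lost patients who in fact died. True mortality is (D + 20f)/200 and the rule (c) estimate is D/180. They are equal when f = D/180. With D = 52 (26% of 200):

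| f | True | Rule (c) |
|---|---|---|
| 0 | 26.0% | 28.9% |
| 0.10 | 27.0% | 28.9% |
| 0.20 | 28.0% | 28.9% |
| 0.289 | 28.9% | 28.9% |
| 0.40 | 30.0% | 28.9% |

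With D = 60 (30% of 200), the rule (c) figure is 60/180 = 33.3% and the break-even is f = 33.3%.

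**Between arms.** If the same fraction of survivors is lost in each arm, the mortality odds ratio does not change. For example, take true rates of 30% and 21% and lose 13% of survivors in each arm: 0.30/(0.30 + 0.70 × 0.87) = 33.0% and 0.21/(0.21 + 0.79 × 0.87) = 23.4%, with an odds ratio of 0.620 before and after. The absolute difference stretches only from 9.0 to 9.6 points. A false difference between arms of equal mortality needs unequal loss. Purely as illustration, with 26% in both arms, none of the lost dead, and loss of 15% against 5%: 0.26/0.85 = 30.6% against 0.26/0.95 = 27.4%, or 3.2 points.

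**The case against.** The case on the other side is substantial. Section 6.1.1 makes ITT primary for every efficacy and safety outcome, and section 7.4.1 tests the secondary hierarchy by ITT, so no conclusion rests on the per-protocol set and no collected outcome is lost to the trial. For the mRS, the complete-case run in section 7.3 already lets a reader separate missed follow-up from rules (a) and (b). Section 7.3 also reports attendance at each visit, so unequal loss would be seen. Section 4.9 requires follow-up to the end of study, so counting a missing day-90 assessment as a deviation is defensible. Reperfusion is scored only in the thrombectomy arm (Table 1, footnote 3), so no between-arm distortion arises there. All of this stands, and it limits the weight of the point.

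A reader might infer more: that per-protocol mortality is too high at both time points, that the arm comparison is biased, and that all 20 patients have day-30 data. The documents support none of these. Dividing true mortality by one minus the loss assumes that no lost patient died. The protocol gives one overall loss figure, with no timing, vital status or split by arm. Even the 3.2-point illustration is small beside a standard error of √(2 × 0.26 × 0.74/100) = 6.2 points at 100 per arm.

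Rule (c) could also be read as applying after the last-value imputation in section 7.3, in which case it would exclude almost nobody. Its exemption for deaths would then be redundant, since section 7.3 already scores deaths, so the plain reading is more likely. None of these arguments gives a reason to drop recorded 24-hour, procedural or 30-day outcomes.

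**Conclusion.** The point holds as a defect in a sensitivity analysis. On its plain reading, rule (c) discards observed outcomes for up to about 20 of 200 patients at the planned loss. For 30-day mortality that number is an upper bound, because patients lost before day 30 have no day-30 status.

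Per-protocol 30-day mortality is biased upward whenever patients known alive at day 30 are lost later, by 0 to 2.2 points at an assumed 20%. For 90-day mortality the bias is upward only if lost patients die less often than retained ones: +2.9 points if none died, zero at about 29%, and downward above that. A spurious treatment difference requires loss that differs by arm, for which the protocol gives no figure. The ITT results and the primary conclusions are not affected.

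**What to change.** In section 6.1.1 and the SAP:

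- Define the per-protocol sample by (a) eligibility violation and (b) treatment crossover only.
- Apply (c) only to the per-protocol analyses of the 90-day mRS, ordinal and 0-2, and say whether missing means before or after imputation.
- For every other outcome, include all patients without (a) or (b) who have that outcome. For 30-day mortality, state what counts as known alive at day 30, since the visit window opens at day 16.
- For 90-day mortality, use Kaplan-Meier estimates censored at the last known-alive contact, and state that this assumes non-informative censoring. This need not bring the figure back to 26%: if all 20 losses came before any of the 52 deaths, the estimate would also be close to 52/180 = 28.9%. Its gain is that it uses the follow-up each lost patient contributed.

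The cost is a short wording change and a per-protocol N that varies by outcome and must be shown in each table. No new data are needed. A smaller form of the same selection remains at day 30 for patients lost before then.

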7.1 Sample Size Estimation for the Primary Outcome

For this study design, power and sample size are computed by assuming that the true proportions of subjects with various mRS outcomes at the 90-day follow-up visit are consistent with the observed OR across all three recently published positive mechanical thrombectomy trials (EXTEND IA = 2.0, ESCAPE = 2.6, MR CLEAN = 1.67), which yields an average OR across all three of 2.1[37-39]. These data were used for the sample size calculation under the proportional odds ordinal logistic model. With the hypothesized OR of 2.1, a total sample size of 180 was estimated to achieve at least 80% power to detect the difference in mRS scores between the control and treatment groups. After accounting a loss of follow-up rate of 10%, the revised POSITIVE trial with a total of 200 patients would provide adequate power with moderate effect size.

7.2 Statistical Evaluation of Primary Endpoint

90-day global disability assessed via the modified Rankin score (mRS), analyzed using raw mRS scores.

Statistical analysis of the primary endpoint will be conducted with a proportional odds ordinal logistic model using raw Rankin scores 0 to 6 (with 5 and 6 collapsed). The stratification variables used in the randomization (NIHSS and center) along with pre-specified potential confounding (prognostic) variables will be adjusted in the analyses. The potential confounding (prognostic) variables include race, age, previous stroke, smoking history, DM, hypertension, and hypercholesterolemia. As a sensitivity analysis, unadjusted analyses will be also performed.

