All of the recent trials reported data randomizing IAT with or without IV-TPA against IV-tPA alone. Given the overwhelming benefit in patients receiving IAT, it is now reasonable to include patients that fail IV-tPA, which also significantly increases the potential to enroll POSITIVE Trial candidates. Many stroke center networks operate where small community hospitals or satellite hospitals are enabled to give IV-tPA through stroke neurology telemedicine systems. These hospitals then usually ship the patients to larger tertiary hospitals where endovascular interventions can be performed, as was frequently done in the MR-CLEAN and ESCAPE trials. This can often create situations where the patient receives IV-tPA at the outside hospital, but by the time they arrive at the tertiary hospital they are beyond the recognized 6 hour time window. Those patients within the 6 and 12 hour time from symptom onset would be eligible for this trial. Patients seen within 6 hours of symptom onset will be immediately considered for endovascular therapy according to the site's standard of care. Likewise, patients presenting beyond 12 hours will be treated according to the site's standard of care. Similarly, the ESCAPE trial showed that patients over 80 years old significantly benefitted from IA therapy just as much as patients younger than 80 years.[39] To better reflect this new clinical reality, there will not be any upper age limitations in the exclusion criteria of POSITIVE.

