Physiologic imaging should also be performed utilizing contrast bolus tracking technique with either MR or CT technologies. Post processing will be as per the institution routine perfusion evaluation, with deconvolution algorithms preferred. Patient selection will be based on the presence of a significant mismatch between the region of infarction depicted on the routine brain imaging scan (extent of CT low attenuation or DWI hyperintensity) and/or low CBV on perfusion maps as per institution standard of care. The viable ischemic penumbra will be determined as the region of tissue at risk as determined on the CBF and MTT (or Tmax) maps minus the region of infarction previously identified. Site-specific perfusion thresholds are to be chosen to include only significant prolongation in transit times or reduction in blood flow, such that minor perfusion changes reflecting benign oligemia are not included in 'at risk' tissue estimates. The qualitative presence of at least 2 color change difference from the normal is considered significant on the color rainbow scale perfusion maps or if quantitative measures are used then an absolute CBV $<2 \text{ ml/100g}$ reflected the infarct core and relative MTT $>145\%$ (or absolute value of >6 seconds) of the contralateral hemisphere most accurately reflected the penumbra. There must be at least 50% volume tissue at risk or an identified eloquent region at risk. The presence of greater than 1/3 territory MCA infarction, ASPECTS <7 or acute infarction greater than 35 cc (from recent data from MR RESCUE trial) volume is considered a boundary for exclusion. Acute volumes will be estimated at the site using $A \times B \times C/2$ calculations.

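### The primary model leaves out infarct extent, occlusion site and IV-tPA receipt, which the trial already assesses at baseline; adding them could gain some power at little cost

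*Combined protocol and SAP*

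**What the plan says.** **Primary model (Section 7.2).** The analysis is a proportional-odds model for 90-day mRS with the two worst levels merged. On covariates it says: "The stratification variables used in the randomization (NIHSS and center) along with pre-specified potential confounding (prognostic) variables will be adjusted in the analyses". It then adds: "The potential confounding (prognostic) variables include race, age, previous stroke, smoking history, DM, hypertension, and hypercholesterolemia". The analysis without covariates is secondary: "As a sensitivity analysis, unadjusted analyses will be also performed".

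**Reason for the covariates.** Section 7 justifies stratifying on NIHSS: "This variable was chosen because of the known association with outcome". No reason is given for the others.

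**Sample size (Section 7.1).** "With the hypothesized OR of 2.1, a total sample size of 180 was estimated to achieve at least 80% power", raised to 200 for 10% loss. No covariate adjustment is described.

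**Variables not in the list.**
- Infarct extent: Section 5.1 sets an exclusion boundary, "The presence of greater than 1/3 territory MCA infarction, ASPECTS <7 or acute infarction greater than 35 cc", with volume estimated at the site by A x B x C/2. Section 5.9.2.1 uses the pretreatment core volume to compute a lesion change for every patient.
- Occlusion site: Section 4.1 requires imaging evidence of an occlusion between the distal ICA and the M1 bifurcation. Section 7.4.2.1 relates functional independence to its location.
- IV-tPA receipt: this bears on eligibility under Section 4.1. The Introduction explains the broadened population: "it is now reasonable to include patients that fail IV-tPA".
- Time from onset: restricted to 6-12 hours by Section 4.1.

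**The concern.** The only reason the plan gives for choosing a baseline variable is its association with outcome. Section 7.4.2.1 puts occlusion location beside NIHSS and age as a correlate of functional independence, yet only NIHSS and age reach the primary model. Infarct extent is central to imaging selection. Patients who failed IV-tPA were brought in by amendment. The covariate list reflects none of this.

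In a proportional-odds model, leaving out a prognostic variable pulls the estimated treatment OR toward 1 and lowers power, even under randomization. Section 7.1 leaves little slack, so a few points of power would be worth having. What is at stake is efficiency, not the validity of the test.

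**Working it through.** **1. The plan's own figure.** The mean of the three published ORs in Section 7.1 is (2.0 + 2.6 + 1.67)/3 = 2.09, used as 2.1. Whitehead's formula is N = 12(z_a/2 + z_b)^2 / [ln(OR)^2 (1 - sum of pbar_k^3)], where pbar_k is the mean proportion across arms at level k. Inputs are two-sided alpha 0.05 (stated only for the secondary endpoints, assumed here), 80% power, 1:1 allocation and six mRS levels.
- 12 x (1.960 + 0.842)^2 / 0.742^2 = 171, before division by (1 - sum of pbar_k^3).
- The documents give no control mRS distribution. With 19%, 25% or 40% of controls at mRS 0-2 (assumed), N is 181, 179 or 177. An extreme 10% gives 189.
- 180/(1 - 0.10) = 200.

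So 180 and 200 reproduce with no covariates in the calculation.

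**2. Simulation set-up.** There were 2,000 trials of n = 180 per scenario, with every model fitted to the same trials. Monte Carlo error is about 1 point for each power. All prognostic strengths and the control mRS distribution are assumptions:
- Log OR per SD of 0.6 for latent NIHSS (entered as a binary stratum) and 0.5 for age.
- Six binary race and vascular factors, with log OR 0 in the table below.
- 20 centers, with center-effect SD 0.2.
- Four omitted factors (infarct extent, site, IV-tPA, time) with combined linear-predictor SD s of 0.3, 0.6 or 0.9.

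To hold the marginal OR at 2.1, the conditional log OR is set to ln(2.1) x sqrt(1 + 0.346v), with v = 0.6^2 + 0.5^2 + s^2 + 0.2^2. For s = 0.6, v = 1.01 and the log OR is 0.742 x 1.162 = 0.862.

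**3. Power (%), without center terms.** Swapped means NIHSS and age plus the four, without the six minor factors.

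| OR of 2.1 taken as | s | Unadjusted | NIHSS + age | Planned list | Planned + four | Swapped |
|---|---|---|---|---|---|---|
| Marginal | 0.3 | 78.6 | 84.1 | 84.1 | 85.3 | 85.3 |
| Marginal | 0.6 | 78.8 | 83.8 | 82.7 | 86.8 | 86.9 |
| Marginal | 0.9 | 79.6 | 82.7 | 82.0 | 90.1 | 89.9 |
| Conditional | 0.3 | 69.5 | 74.1 | 74.6 | 75.5 | 75.6 |
| Conditional | 0.6 | 65.9 | 71.3 | 70.8 | 74.0 | 74.7 |
| Conditional | 0.9 | 60.0 | 64.8 | 65.1 | 73.1 | 74.1 |

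- Adding the four to the planned list gains 1.2, 4.1 and 8.1 points (marginal) or 0.9, 3.2 and 8.0 (conditional). Swapping gains 1.2, 4.2 and 7.9, or 1.0, 3.9 and 9.0.
- NIHSS and age alone gain about 3 to 6 points over the unadjusted model.
- The six minor factors cost at most about 1 point (83.8 to 82.7) even with no prognostic value. If they have log OR 0.2 (marginal, s = 0.6), adding gives 87.4 and swapping 86.5, so keeping them does no harm.
- With the conditional OR fixed at 2.1, the mean estimated OR under the planned list is 2.10, 2.03 and 1.94 as s rises. With the four added it stays at 2.15.

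**4. Type I error.** Under the null at s = 0.6, rejection was 5.6% for the planned list, 6.0% with the four added and 5.7% when swapped. Monte Carlo error is sqrt(0.05 x 0.95/2000) = 0.5 points, so the omission does not inflate error.

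**5. Why center is left out of the comparison.** Section 7.2 does not say how center enters. Twenty indicator terms raised null rejection to 7.4%, so power figures with them are not comparable. The planned list then had 82.4, 82.0 and 81.2% (marginal).

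**The case against.** The strongest reply is that the plan already adjusts for NIHSS, center and age, and that nothing in the documents shows the missing variables to be strong predictors.

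- Eligibility narrows them: ASPECTS at least 7, core up to 35 cc, distal ICA to M1, 6-12 hours.
- For time, Section 2.1 reports good outcome of 42.8% vs 41.9% around a median of 8 hours (p = 1.0), and 30.2% vs 45.5% around 7 hours (p = 0.1, numerically favoring later treatment). Both are series of treated patients.
- For IV-tPA, the Introduction describes weak effect on large-vessel occlusions, which does not suggest a large difference in prognosis.
- Changing the primary covariates during a trial that is open apart from outcome assessment has its own risk.

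Most of this stands. It makes the low end of the gain plausible, makes time optional and calls for a safeguard on the change. It does not remove the case for infarct extent and occlusion site. The further objection that core size may go unrecorded is met by Section 5.9.2.1, which needs a pretreatment core volume for each patient.

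A reader might infer more than the documents support:
- That the listed covariates are weak and bring no gain. The documents do not rank prognostic strength, and NIHSS and age do bring a gain in the simulation.
- That chance imbalance in an omitted factor biases the trial. Randomization holds, and the standard error already reflects such imbalance. Adjustment improves precision.
- That the amendment simply made the population more mixed. It added IV-tPA failures and moved the late cohort from 8-12 to 6-12 hours, but it also ended enrollment within 6 hours.

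**Conclusion.** The point holds as one of efficiency. The 7.2 model omits baseline variables already in hand, and a fuller model would probably have somewhat more power. Under the assumed strengths the gain over the planned model without center terms is about 1 point at SD 0.3, 3 to 4 at 0.6 and 8 to 9 at 0.9. The documents do not fix where the truth lies.

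The simulated set includes time. If the four contribute equally, as simulated, three of them have a combined SD of sqrt(3/4) = 0.87 times the stated value, so the gain without time would be somewhat smaller.

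The conditional rows of the table might tempt a reader to conclude that the omission breaks the 80% claim. It does not. Section 7.1 describes no adjustment, and its figure reproduces as a calculation without covariates. On the conditional reading even the fuller models reach only 73 to 76%, so that shortfall comes mainly from how the OR of 2.1 is read. Type I error is unaffected. Low to moderate priority.

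**What to change.** Before database lock, and with the decision made by people who have no access to outcome data by arm, add three terms to the 7.2 list:
- Pretreatment core volume, as one measure for both CT- and MR-selected patients. State whether it is the site estimate of Section 5.1 or the semi-automated reading of Section 5.9.2.1.
- Occlusion site, ICA vs M1.
- IV-tPA receipt, yes or no.

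Time from onset to randomization may be added but is optional. Keep all existing covariates, and report the present 7.2 list as a sensitivity analysis beside the unadjusted one.

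The cost is an amendment to the analysis text, three more parameters (four with time) and a rule for missing core volumes. Site-estimated volume carries measurement error, which will reduce the gain from that term.
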